9 SAFETY DATA MANAGEMENT

9.1 Adverse Event (AE)

An AE is defined as any untoward medical occurrence in a patient or clinical investigational patient administered a medicinal product, which does not necessarily have a causal relationship with this treatment.

An AE can therefore be any unfavorable and unintended sign (including an abnormal laboratory finding), symptom, or disease temporally associated with the use of a medicinal product, whether or not considered related to the medicinal product.

9.2 Drug Relationship

The relationship between an AE and study drugs will be judged according to the following categories:

- **Certain**: The AE occurs in a plausible time relation to the administration of the drug and cannot be explained by a concurrent disease or other drugs or chemicals. The response to withdrawal of the drug (dechallenge) should be clinically plausible. The event must be definitive pharmacologically or phenomenologically, using a satisfactory rechallenge procedure if necessary.
- **Probable:** The AE occurs in a reasonable time relation to the administration of the drug; it is unlikely to be attributed to a concurrent disease or other drugs or chemicals and it follows a clinically reasonable response on withdrawal (dechallenge).

REVARIN	Global Medical Department		
		Protocol Template	
Identification Number	Version Number	State	Effective date
FORM-000050125	3.0, CURRENT	Effective	13 May, 2022

Rechallenge information (AE reappearance after drug reintroduction) is not required to fulfill this definition.

- **Possible**: The AE occurs with a reasonable time relation to the administration of the drug, but it could also be explained by a concurrent disease or other drugs or chemicals. Information on drug withdrawal (dechallenge) may be lacking or unclear.
- **Unassessable:** The relationship cannot be judged, because of the information is insufficient or contradictory and cannot be supplemented or verified.
 - **Unlikely**: A causal relationship cannot be definitively ruled out, but:
 - other drugs, chemicals, or underlying disease provide plausible explanations and / or
 - the temporal relation to the administration of the drug makes a causal relation improbable.
- Not Related: Any of the following are present:
 - existence of a clear alternative explanation, and / or
 - unreasonable temporal relationship between Drug and Event, and / or
 - non-plausibility.

9.3 Adverse Drug Reaction (ADR)

An ADR is any untoward and unintended response to an IMP related to any dose administered.

The definition implies a reasonable possibility of a causal relationship between the event and the IMP. This means that there are facts (evidence) or arguments to suggest a causal relationship.

An ADR is considered any AE for which the relationship is considered as:

- 1. Certain
- 2. Probable
- 3. Possible
- 4. Unassessable
- An AE is not considered as ADR when the relationship is judged as:
 - 1. Unlikely
 - 2. Not related

9.4 Seriousness

An AE / ADR is considered serious when:

- 1. Results in death.
- 2. Is life-threatening.

REVARIN	Global Medical Department		
		Protocol Template	
Identification Number	Version Number	State	Effective date
FORM-000050125	3.0, CURRENT	Effective	13 May, 2022

Note: Life-threatening is considered as any AE in which the patient was at risk of death at the time of the event; it does not refer to an event which hypothetically might have caused death if it were more severe.

- requires inpatient hospitalization or prolongation of existing hospitalization.
- results in persistent or significant disability / incapacity.
- is a congenital anomaly / birth defect.
- is another medically important condition that may jeopardize the patient or may require intervention to prevent one of the outcomes listed above. Any suspected transmission of an infectious agent via a medicinal product is considered serious and should be assessed under the category of medically important events in the absence of other seriousness criteria.

An AE/ADR is considered non-serious when it does not fulfill the conditions for the definition of Serious AE/ADR.

9.5 Adverse Event/Adverse Drug Reaction Intensity

Investigators must assess the severity/intensity of a Serious or a Non-serious AE or ADR and attributed according to the following definitions:

- **Mild:** does not interfere with routine activities; in case of laboratory tests when there is a mild abnormality.
- **Moderate**: interferes with the routine activities; in case of laboratory tests when there is a moderate abnormality.
- Severe: makes it impossible to perform routine activities; in case of laboratory tests when there is a significant abnormality.

9.6 Adverse Event/Adverse Drug Reaction Expectedness

An AE/ADR is considered Unexpected when the nature, severity, or outcome of the AE/ADR is not consistent with the information provided in the Reference Safety Document (to be specified: SmPC).

9.7 Serious Unexpected Adverse Drug Reaction (SUSAR)

Any SAE judged by the Investigator or the Sponsor as drug-related (see Section 9.3) and considered as unexpected qualifies as a SUSAR.

SUSARs are subject to expedited reporting, as specified in Section 9.10, as having a "Reasonable Possibility" of relationship with the IMP.

REVARIN	Global Medical Department		
		Protocol Template	
Identification Number	Version Number	State	Effective date
FORM-000050125	3.0, CURRENT	Effective	13 May, 2022

9.8 Individual Case Safety Report (ICSR)

Format and content provided to describe one or several AEs or a disease experience that occur to an individual patient at a particular point of time.

9.9 Collection, Recording and Reporting of AEs

At each visit, the Investigator will collect and assess any subjective or objective AE occurred to each patient after his/her signature of the informed consent.

Any AE (or adverse experience) occurring prior to first IMP administration should be considered as medical history or pre-existing conditions and should be recorded on the Medical History/Pre-existing eCRF page and not on the AE page.

Any clinically significant laboratory test results observed after informed consent signature and prior to first IMP administration, should be recorded in Lab Test page of the eCRF, and must not be considered as an AE.

The Investigator should manage as AE any laboratory test abnormality (newly occurring after the IMP administration or worsening of previously known abnormalities) considered as clinically relevant: i.e., values significantly above or under normal range or which require an intervention or diagnostic tests or may result in the IMP discontinuation.

Any AE communicated by the patient or by the patient's relatives or delegates through phone calls, letters or e-mails will also be collected and assessed.

The Investigator shall record on the respective eCRF AE pages, any recognized AE identifying an ICSR, occurred after IMP administration, both serious and non-serious, whether or not thought to be drug-related, observed in or reported by the patient (or relatives/delegates), specifying the judgment on the causal relationship with the study treatment (monotherapy or extemporaneous combination).

Any available information and diagnostic measure (laboratory and instrumental tests, procedures, etc.) shall be recorded in and/or attached to the concerned CRF pages/sections. The Investigator is expected to also record any AE which was ongoing at the last treatment dose and a follow-up phone call should be made after 2 weeks from the last study visit. The Investigator is expected to follow up any AE occurred during the study, including the follow-up period, until the outcome of the AE has been determined.

The Investigator must report all the collected information on any ICSR with Serious and Non-Serious AE (whether or not thought to be related to the investigational drug), providing the concerned eCRF AE pages by alert e-mail, after the first knowledge of the occurrence of the case, to:

REVAINS	Glol	oal Medical Department	
	Protocol Template		
Identification Number	Version Number State Effective date		Effective date
FORM-000050125	3.0, CURRENT	Effective	13 May, 2022

CRO Pharmacovigilance Officer: Will be reported through CRO's Pharmacovigilance ([contact]) group for which its details will be provided via study guidelines.

The eCRF pages concerning IMP, medical history, concomitant medication, and laboratory tests should also be sent to the Sponsor by e-mail.

9.10 Management of Serious AEs (SAEs) including laboratory abnormalities

9.10.1 Reporting Duties of the Investigator

The Investigator must report all the collected information on any ICSR with SAE (whether or not thought to be related to the investigational drug), as above specified, no later than 24 hours after the first knowledge of the occurrence of the case.

Any further information and supporting documentation that become available (copies of laboratory reports, tests, procedures, autopsy evidence of the cause of death, etc.) shall be provided no later than 24 hours after the knowledge, by the Investigator to the CRO by alert e-mail, to be forwarded to the Sponsor.

The Investigator must also comply with the local applicable obligation(s) on the reporting of ADRs to the local concerned Regulatory Authority/EC.

9.10.2 Reporting Duties of the Sponsor

The Sponsor shall ensure that all relevant information about any SUSAR, is expeditiously reported to the competent HAs and EC as required, with these deadlines after the first knowledge, intended as the day when the CRO receives the notification of the SUSAR:

- Fatal and life-threatening unexpected cases, no later than 7 days.
- Other unexpected serious cases, no later than 15 days.

The Sponsor shall ensure that all relevant information and supporting documentation that subsequently becomes available, is also expeditiously reported as follow-up information according to the above-mentioned deadlines.

When the study is blinded, the patient's code will be broken before the expedited reporting to the competent HAs and the EC.

Furthermore, the following safety issues will be subjected to expedited management for the identification of possible necessary actions:

- SAEs associated with the trial procedures.
- Potential clinically significant findings emerging from non-clinical studies.
- An anticipated end or suspension for safety reasons of another trial with the same study drug.

When appropriate and applicable the Sponsor will arrange the adequate information to be communicated to the Investigators.

RENARIN	Global Medical Department Protocol Template		
Identification Number	Version Number	State	Effective date
FORM-000050125	3.0, CURRENT Effective 13 May, 20		13 May, 2022

For trials in high morbidity and/or mortality disease, where efficacy endpoint could also be Serious Unexpected ADRs or when a fatal or other serious outcome is the primary endpoint, agreement with competent HA will be reached to treat SAE as disease-related and not subject to expedited reporting.

9.11 Management of Non-serious AEs including laboratory abnormalities

9.11.1 Reporting Duties of the Investigator

The Investigator must report all the collected information on any ICSR with non-SAE (whether or not thought to be related to the investigational drug), as above specified, no later than 5 Calendar days after the first knowledge of the occurrence of the case. Any further information and supporting documentation that become available (copies of laboratory reports, tests, procedures, etc.) shall be provided no later than 24 hours after the knowledge, by the Investigator first becomes aware, to the CRO by e-mail or fax, to be forwarded to the Sponsor.

9.12 Management of any laboratory abnormality

Any laboratory test abnormality which is considered by the Investigator as AE is to be managed as above detailed (refer to Section 9.9).

However, all "out of range" values should be collected and reviewed periodically by the CRO and the Sponsor.

9.13 Management of pregnancy exposure cases

The Investigator is expected to record in the provided form any case of pregnancy exposure occurring in a female patient or in a male patient's partner during the treatment and follow-up periods, sending it within 5 days after being made aware of the pregnancy, to the CRO by e-mail or fax, to be forwarded to the Sponsor.

The Investigator is requested to follow each case of pregnancy exposure until the outcome. If the pregnancy results in an abnormal outcome, this will be recorded in the CRF as a SAE and managed as above described.

Eligibility of a woman of childbearing potential (WOCBP) will be considered as described in Section 6.2.1. A woman is considered fertile following menarche and until becoming postmenopausal unless permanently sterile as described below.

Women in the following categories are not considered WOCBP if:

- Premenarchal
 - Premenopausal female with one of the following:
 - o Documented hysterectomy.
 - o Documented bilateral salpingectomy.

CONFIDENTIAL

•

REVARIN	Global Medical Department Protocol Template		
Identification Number	Version Number	State	Effective date
FORM-000050125	3.0, CURRENT	Effective	13 May, 2022

o Documented bilateral oophorectomy.

Note: Documentation can come from the study site personnel's review of the patient's medical records, medical examination, or medical history interview.

• Postmenopausal female: A postmenopausal state is defined as no menses for 12 months without an alternative medical cause. A high follicle stimulating hormone (FSH) level, to 30 mIU/mL or higher may be used to confirm a postmenopausal state in women not using hormonal contraception or hormonal replacement therapy (HRT). However, in the absence of 12 months of amenorrhea, a single FSH measurement is insufficient. Females on HRT and whose menopausal status is in doubt will be required to use one of the non-estrogen hormone, highly effective contraception methods if they wish to continue their HRT during the study. Otherwise, they must discontinue HRT to allow confirmation of postmenopausal status before study enrolment.

REVARIN	Gloi	bal Medical Department	
	Protocol Template		
Identification Number	Version Number	State	Effective date
FORM-000050125	3.0, CURRENT Effective 13 May, 202		13 May, 2022

10 WITHDRAWAL CRITERIA

Patients may discontinue the study product, but remain in the study for follow-up, especially for safety and study endpoints (if applicable).

Withdrawal from the study treatment

Withdrawal from the study treatment (monotherapy or extemporaneous combination therapy) refers to any patient who does not receive the complete course, i.e., when no further planned dose is administered from the date of withdrawal. A patient withdrawn from the study treatment may continue further study procedures (safety) planned in the Study Protocol, as deemed appropriate by the Investigator once the safety of the patient is recovered/reassured. A patient's study treatment (monotherapy or extemporaneous combination therapy) may be discontinued for any of the reasons listed below:

- Any AE, which required treatment termination according to the Investigator's judgment.
- Clinically significant intercurrent illness or laboratory results which could compromise the safety of the patient or the scientific value of the study.
- Investigator deems it to be in the best interest of the patient to discontinue.
- Requirement to use prohibited medication that could compromise the safety of the patient or the scientific value of the study.

In addition to the scheduled visits, patients who have been withdrawn from study treatment (monotherapy or extemporaneous combination therapy) may also undergo additional medical follow-up at the discretion of the Investigator.

Withdrawal of patient from the study

The patient may withdraw from the study at any time without explanation, without losing the right to future medical care. The participation of the patient may, at any moment, be terminated by the Investigator, if considered appropriate.

A patient can be withdrawn during the study for any of the following reasons:

- Any AE, which required treatment and study termination for the patient according to the Investigator's judgment.
- Abnormal renal function (creatinine clearance < 30 mL/min) or abnormal liver enzyme parameters (alanine aminotransferase or aspartate aminotransferase level of > 2.5 × upper limit of normal [ULN] or total bilirubin level > 1.5 × ULN) as described in Table 2.
- Patient becomes pregnant during the study.
- Request of the patient (without giving any reason).
- Investigator deems it to be in the best interest of the patient to discontinue.
- Failure to adequately comply with the dosing, evaluations, or other requirements of the study.

REVARIN	Glol	oal Medical Department	
	Protocol Template		
Identification Number	Version Number	State	Effective date
FORM-000050125	3.0, CURRENT	Effective	13 May, 2022

- If the patient meets an exclusion criterion (newly developed or not previously recognized) that precludes further study participation.
- Use of any prohibited medication that in the opinion of the Investigator or Sponsor necessitates the patient being withdrawn.

The reason for the withdrawal of study treatment, or withdrawal from the study must be well documented in the source documents and in the eCRF page and should capture the date and the specific underlying reason for discontinuation of study treatment or patient discontinuation/withdrawal.

Patients who discontinue from the study early will be asked, anyway, to complete all the assessments of Visit 5. Patients may discontinue the study treatment, but remain in the study for follow-up, especially for safety study endpoints (if applicable).

If a patient has been discontinued/withdrawn due to an AE, the Investigator must immediately notify the relevant pharmacovigilance contact (see Section 9.9) and should be followed-up until the AE is resolved or the Investigator deems further observations or examinations as no longer medically indicated.

11 LOST TO FOLLOW UP

A patient will be considered lost to follow-up if he/she fails to return for the scheduled visits and is unable to be contacted by the study site staff.

The site will attempt to contact the patient and reschedule the missed visit and counsel the patient on the importance of maintaining the assigned visit schedule and ascertain if the patient wishes to and/or should continue in the study.

Before a patient is deemed lost to follow-up, the Investigator or designee will make every effort to regain contact with the patient. These contact attempts should be documented in the patient's medical record or study file.

12 STATISTIC

12.1 Statistical Methods (Blinding and Randomization)

This is an open-label study. In this study all the patients will receive monotherapy in the Run-in period and combination therapy in the study Assessment period. No randomization will be required.

REVARIN	Glol	oal Medical Department	
	Protocol Template		
Identification Number	Version Number	State	Effective date
FORM-000050125	3.0, CURRENT	Effective	13 May, 2022

12.2 Determination of Sample Size

A sample size of 215 achieves 90% power to detect a Systolic BP difference of -2.4 mmHg between the null hypothesis mean of 3.0 mmHg and the alternative hypothesis mean of 5.4 mmHg with a known standard deviation of 12.0 mmHg and with a significance level (alpha) of 0.05 using a one-sided one-sample t-test. Such a difference in SBP is highly clinically significant in a population-wide perspective since, as clearly demonstrated by Hardy et al²⁰, if applied nationwide, a hypothetical 1 mmHg shift in SBP among African American and white US populations aged 45 to 64 years was estimated to prevent \approx 9338 incident heart failure events, 6210 incident coronary heart disease events, and 3761 incident stroke events annually, while the hypothetical intervention achieving the larger SBP reduction of 2 mmHg was associated with larger reductions in the incidence of coronary heart disease, stroke, and heart failure for both racial groups.

A total number of 270 patients will be screened considering a screen failure/drop-out rate of 20%, to obtain at least 215 completed patients at the EoS (Visit 5) (patients who complete all visits including EoS Visit [Visit 5]).

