Statistical Assumptions	The primary endpoint will be assessed before and after Assessment period at Week 12, by a paired t-test using the Modified Intent-to-Treat population and the Per-Protocol population. A sample size of 215 achieves 90% power to detect a Systolic BP difference of -2.4 mmHg between the null hypothesis mean of 3.0 mmHg and the alternative hypothesis mean of 5.4 mmHg with a known standard deviation of 12.0
	mmHg and with a significance level (alpha) of 0.05 using a one-sided

NENARINI	Glo	bal Medical Department	
	Protocol Template		
Identification Number	Version Number	State	Effective date
FORM-000050125	3.0, CURRENT	Effective	13 May, 2022

Γ	
	one-sample t-test. Assuming an approximate 20% screen failure/drop-
	out rate, two-hundred and seventy (270) patients with uncontrolled
	hypertension are planned to be screened to obtain at least 215 completed
	patients at the end of the study (Visit 5) (patients who complete all visits
	including EoS Visit [Visit 5]). Hypothesis about the direction of the
	treatment effect: one-sided test has more statistical power to detect an
	effect in one direction because it is expected that combination therapy
	increases treatment efficacy in patients with uncontrolled hypertension
	previously treated with NEB or RAM monotherapies for at least 30 days.
	In this scenario, it is possible to exclude the hypothesis of testing the
	possibility that the combination therapy is less effective than the
	monotherapy, for this reason a one-sided test is more appropriate.

NENARINI	Glo	bal Medical Department	
	Protocol Template		
Identification Number	Version Number	State	Effective date
FORM-000050125	3.0, CURRENT	Effective	13 May, 2022

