To correctly evaluate the additional effect of the combination therapy, the number of patients with uncontrolled BP on NEB or RAM monotherapy needs to be balanced at Visit 2. To maintain a 1:1 ratio during the Assessment period, a cap of 110 patients for each treatment arm (i.e., NEB and RAM) will be included at Visit 2 to maintain a balanced number of uncontrolled patients entering the Assessment period for each drug. The evaluation will be done every 50 patients. If the entrance in the Assessment period for 1 of the 2 tested drugs will deviate more than 5%, a corrective measure will be initiated: according to the enrolment site statistics, 1 or more sites will be informed to enroll a greater number of patients being treated with the least represented drug in the Assessment period.

A total number of 270 patients will be screened considering a screen failure/drop-out rate of 20%, to obtain at least 215 completed patients at the end of the study (Visit 5) (patients who complete all visits including EoS Visit [Visit 5]).

Sitting BP will be measured at all visits before blood sampling. Blood Pressure will be measured in both arms at the Screening Visit (Visit 1) to detect possible between-arm differences. Three BP measurements will be performed for each arm. The arm with the higher mean DBP will be identified at screening and will be used in all subsequent visits for BP assessment. Blood pressure measurements should be performed as nearly as possible within the same time frame of the day (7:00 a.m. to 12:00 p.m.), on the same arm, possibly by the same trained member of the site staff/personnel and using the same calibrated automated device, provided by the Sponsor, at each visit.

Patients should be seated comfortably in a quiet environment for 5 minutes before beginning BP measurements. Three BP measurements will be recorded, 1 to 2 minutes apart, and CONFIDENTIAL Page 36 of 90

RENARIN	Glot	bal Medical Department	
	Protocol Template		
Identification Number	Version Number	State	Effective date
FORM-000050125	3.0, CURRENT	Effective	13 May, 2022

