12.5 Statistical Analysis

Descriptive statistics

Patient disposition, demographics and baseline characteristics will be summarized for monotherapy and combination therapy. Medical history will be summarized only for monotherapy. Prior and concomitant medications will be summarized for combination therapy (NEB + RAM).

Continuous variables will be summarized using the number of non-missing observations, mean, SD, minimum, median, and maximum values. Categorical variables will be presented with the number of non-missing observations and column percentages (n, %).

Primary (efficacy) analysis

The primary efficacy analysis will be conducted on the mITT population. The results will be interpreted for the same population.

The primary endpoint is the change in mean sitting SBP between Visit 2 (Week 0) and Visit 5 (Week 12).

The statistical hypothesis will be defined as below:

H0: There is no change in the sitting SBP post combination therapy.

H1: There is a difference in the sitting SBP post combination therapy.

The above hypothesis will be tested as following:

- Change from baseline in sitting SBP from prior and post combination therapy will be tested using paired t-test. The p-value obtained from the paired t-test will be presented.
- Assumption of Normality will be investigated using Wilk-Shapiro test. If the data is found to be non-Normal, the paired t-test will be replaced by Wilcoxon signed rank test.
- The primary endpoint will be summarized descriptively using n, mean, median, SD, Q1 (first quartile), Q3 (third quartile), minimum, and maximum.

MENARIN	Global Medical Department		
	Protocol Template		
Identification Number	Version Number	State	Effective date
FORM-000050125	3.0, CURRENT	Effective	13 May, 2022

Sensitivity analysis

The sensitivity analyses will be conducted using the PP population.

The PP population will be used to assess the robustness of the results obtained using the mITT population.

Secondary (efficacy) analysis

Secondary efficacy variables will be summarized in a descriptive manner using the mITT population.

- Change in mean sitting DBP between Visit 2 (Week 0) and Visit 5 (Week 12).
- Change in mean sitting DBP and SBP between:
 - Visit 2 (Week 0) and Visit 3 (Week 4)
 - Visit 2 (Week 0) and Visit 4 (Week 8)
- Number and proportion of patients achieving the standard BP goal (sitting BP < 140/90 mmHg) at Visit 5 (Week 12).

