12.6 Protocol Deviations and Protocol Amendments

No deviations from the Study Protocol should be initiated without prior approval by EC/HA of a Protocol Amendment according to applicable regulations, except in case of emergency or when the change involves only logistical or administrative aspects of the trial.

Any deviation from the Study Protocol, SOPs, Good Clinical Practice (GCP) and applicable regulatory requirements should be immediately reported to the Sponsor.

Changes in the Study Protocol will require a Protocol Amendment. Such amendments will be agreed upon and approved in writing by all signatories of the protocol.

If amendments are substantial, i.e., are likely to have an impact on the safety of the subjects, or to change the interpretation of the scientific documents in support of the conduct of the study, or if they are otherwise significant, the ECs and the competent HAs in the participating countries must approve these amendments before implementation, according to applicable regulatory requirements.

Changes which have no significant impact on medical or scientific validity of the study will be agreed upon and approved in writing by all signatories of the protocol and the EC will be notified of this Protocol Amendment.

Any substantial amendments of the protocol will be integrated in an updated Study Protocol. The Principal Investigator must ensure full adherence with the updated Study Protocol.

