12.7 Statistical Analysis Plan

This study is an open-label study and statistical analysis plan (SAP) will be written prior to first patient in and before any statistical activities are performed. However, the SAP will be finalized prior to database lock. The SAP will describe in detail study endpoints and statistical analyses, including the analysis of the primary as well as additional endpoints. In case changes to the original primary endpoint or of the original primary analyses occurs during the study, these changes will be the subject of a substantial Protocol Amendment. All statistical analyses not prespecified and run after database lock will be considered additional/exploratory analyses.

MENARIN	Global Medical Department		
		Protocol Template	
Identification Number	Version Number	State	Effective date
FORM-000050125	3.0, CURRENT	Effective	13 May, 2022

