The evaluation will be done every 50 patients. If the entrance in the Assessment period for 1 of the 2 tested drugs will deviate more than 5%, a corrective measure will be initiated: according to the enrolment site statistics, 1 or more sites will be informed to enroll a greater number of patients being treated with the least represented drug in the Assessment period.

A total number of 270 patients will be screened, to obtain at least 215 completed patients at the end of the study (Visit 5) who have at least baseline and Week 12 assessments with primary efficacy data. For the sample size justification refer to section 12.2 of study protocol version 3.0.

Sitting BP will be measured at all visits before blood sampling. Blood Pressure will be measured in both arms at the Screening Visit (Visit 1) to detect possible between-arm differences. Three BP measurements will be performed for each arm. The arm with the higher mean DBP will be identified at screening and will be used in all subsequent visits for BP assessment. Blood pressure measurements should be performed as nearly as possible within the same time frame of the day (7:00 a.m. to 12:00 p.m.), on the same arm, possibly by the same trained member of the site staff/personnel and using the same calibrated automated device, provided by the Sponsor, at each visit.

Patients should be seated comfortably in a quiet environment for 5 minutes before beginning BP measurements.

Three BP measurements will be recorded, 1 to 2 minutes apart, and additional measurements only if the first 2 readings differ by >10 mmHg. The mean of the 3 recordings in sitting position will be used as the BP value for that visit. All BP measurements during the treatment phase will be performed as through readings (i.e., 24 + 2 hours after the last drug intake) using the same calibrated automated device, provided by the Sponsor. Study medication should be taken on the same time every day during the study; except the days of site visits, when study medication should be taken at the study center after all assessments mentioned as per study flow chart. At Visit 1 (Week -4) and Visit 5 (Week 12), a 12-lead ECG will be performed.

Safety (AEs, SAEs) will be measured at all visits. Any patient having an ongoing AE or SAE at the last visit, will be followed-up for further 2 weeks through a phone call to check about the status of the AE/SAE.

Page 16 of 46

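### The stated 90% power belongs to a one-sided test against a 3.0 mmHg null, not to the planned two-sided test of no change in SBP

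*Protocol*

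**What the plan says.** Protocol 12.2 states: "A sample size of 215 achieves 90% power to detect a Systolic BP difference of -2.4 mmHg". That difference is the distance "between the null hypothesis mean of 3.0 mmHg and the alternative hypothesis mean of 5.4 mmHg with a known standard deviation of 12.0 mmHg", at a one-sided alpha of 0.05. The synopsis repeats the calculation. It argues that the combination need not be tested for being worse than monotherapy, and concludes "for this reason a one-sided test is more appropriate".

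The analysis sections describe another test:

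- Protocol 12.5 sets "H0: There is no change in the sitting SBP post combination therapy" against an alternative with no direction, by paired t-test, replaced by the Wilcoxon signed-rank test if Shapiro-Wilk indicates non-normality. It gives no sidedness for the primary test. For the secondary BP changes it specifies two-sided tests at 5%.
- SAP 16.1.3 keeps the no-change null and the undirected alternative, and asks for a 2-sided p-value.
- SAP 6.5 sets 5% two-sided tests as the default.
- The SAP reference code (Appendix 1) sets the null to zero for both the paired t-test and the signed-rank test.

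On sample size, SAP 3.1 sends the reader back: "For the sample size justification refer to section 12.2 of study protocol version 3.0". SAP 3.3, on changes from the planned analysis, covers only Sites 114 and 507. No section says what 3.0 mmHg represents.

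**The concern.** The sizing test and the planned test differ in both null value and sidedness, so the quoted power is that of a test nobody will run. Two consequences follow.

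First, the power statement is wrong, and the direction of the error depends on which of the protocol's figures is the expected change from baseline. Second, a reader of Protocol 12.2 may take a significant primary result to mean that the fall in SBP has been shown to exceed 3.0 mmHg. A test against zero cannot show that.

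The mismatch does not threaten the validity of the primary test. Testing zero fits the stated objective, the mismatch inflates no error rate, and it does not bias the estimate.

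**Working it through.** **Inputs.** From Protocol 12.2: n = 215, SD 12.0 mmHg, null mean 3.0, alternative mean 5.4, alpha 0.05 one-sided. From the SAP: null 0, alpha 0.05 two-sided. I read the means as falls in SBP.

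**Formulas.** SE = SD/√n = 12/√215 = 0.8184 mmHg. By normal approximation, power = Φ(δ/SE − z), where δ is the distance of the true mean from the null. The exact figures use the non-central t distribution with n − 1 degrees of freedom.

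**1. The protocol's own figure.** δ = 5.4 − 3.0 = 2.4, so δ/SE = 2.93. One-sided: Φ(2.93 − 1.645) = 90.1%, exact 89.9%. The stated 90% reproduces.

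**2. The planned test: null 0, two-sided 5%, n = 215.**

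| True fall (mmHg) | δ/SE | Power, normal | Power, exact t |
|---|---|---|---|
| 5.4 (stated alternative mean) | 6.60 | >99.9% | >99.9% |
| 3.0 (stated null mean) | 3.67 | 95.6% | 95.4% |
| 2.4 (stated difference) | 2.93 | 83.5% | 83.1% |

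The fall detectable with 90% power is about 2.7 mmHg (2.66 exact).

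**3. Smallest observed fall that is significant, if the observed SD is 12.** Planned test: 1.971 × 0.8184 = 1.61 mmHg. Sizing test: 3.0 + 1.652 × 0.8184 = 4.35 mmHg.

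**4. Sensitivity to the number analysed.** SAP 5.2 removes Site 114 and some Site 507 patients from the mITT set, and the documents give no count. At an assumed 200 or 180 analysed, power at 2.4 mmHg is 80.4% or 76.1%. At 5.4 mmHg it stays above 99.9%.

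**5. Sensitivity to the SD.** At a true fall of 5.4 mmHg and n = 215, two-sided power stays at or above 90% until the SD of the change reaches about 24.4 mmHg, roughly twice the planning value.

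**6. Signed-rank fallback.** All these powers are for the t-test. As a rough guide under normality, the signed-rank test has efficiency 3/π, so 215 patients act like 215 × 3/π ≈ 205. That gives about 81.3% at 2.4 mmHg and above 99.9% at 5.4. The fallback is used when normality is rejected, so these values are only indicative.

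**The case against.** The best defence is that little turns on this. The test is valid, the two-sided 5% level is stricter than the one-sided level the synopsis argues for, and no objective or analysis section defines success as a fall above 3.0 mmHg. All of that stands. It limits the point to a wrong planning statement and a risk of misreading.

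Two stronger readings are tempting, and the documents do not support either.

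- **That the trial is underpowered.** A reader might take 83.1% as the true power and note that 90% at 2.4 mmHg needs 265 analysed, when the protocol says "a cap of 110 patients for each treatment arm (i.e., NEB and RAM) will be included at Visit 2", or 2 × 110 = 220 in total. That requires 2.4 mmHg to be the change from baseline. Protocol 12.2 defines it as the gap between 3.0 and 5.4 mmHg. At the protocol's own alternative mean, power against zero is above 99.9%. The 2.4 mmHg reading is still arguable, because 12.2 goes on to defend a difference of that size as clinically important, so both figures should be given.
- **That the SAP changed the protocol's primary test without disclosure.** The alternative in Protocol 12.5 has no direction, and the SAP's two-sided test is consistent with it. The inconsistency lies mainly inside the protocol, between 12.2 with the synopsis and 12.5. The SAP inherits it by pointing back to 12.2.

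**Conclusion.** The 90% power does not describe the planned primary test, and no section reconciles the two. With the paired t-test, n = 215 and the planning SD of 12 mmHg, 90% understates power if 5.4 mmHg is the expected fall (above 99.9%). It overstates power only if 2.4 mmHg is taken as the change from baseline (about 83%). A significant result could arise from an observed fall of about 1.6 mmHg. It would support a non-zero change, not one above 3.0 mmHg.

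These figures assume that the planning SD holds, that about 215 patients are analysed, and that the t-test rather than the signed-rank fallback is used. This is an inconsistency worth correcting before lock, not a flaw in the test or a case for more patients.

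**What to change.** Keep the two-sided test of zero and the patient number. Before database lock:

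1. Record in the SAP (3.3 is the natural place) and in the clinical study report that n = 215 was derived for a different test, with a 3.0 mmHg null and one-sided 5%. Leave that original basis visible.
2. Restate the power of the planned paired t-test at the protocol's own effects: above 99.9% at 5.4 mmHg and about 83% at 2.4 mmHg, for n = 215 and SD 12. Note that these figures do not strictly apply if the signed-rank test is used. Do not compute power from the observed change.
3. Report the mean SBP change with its 95% CI, and say that significance supports only a non-zero change. SAP 6.5 sets a 95% level for intervals, but the summary list in 16.1.3 contains none.

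**Cost.** One SAP revision and a short statement in the report. The table shells are not in the documents, so they may already carry the interval. If they do not, SAP 4 requires a SAP amendment to change them, and the same revision can serve.

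Correcting the protocol text costs more: "Changes in the Study Protocol will require a Protocol Amendment" (Protocol 12.6), with written approval by all signatories and at least notification of the ethics committee.

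If the sponsor does intend a 3.0 mmHg null, it should explain that value and change the hypothesis, test and code to match. Protocol 12.7 says of changes to the primary analysis that "these changes will be the subject of a substantial Protocol Amendment". Stated power would then be 89.9% one-sided or 83.1% two-sided at 5.4 mmHg, in place of above 99.9%. It would also be a late change in an open-label trial: SAP version 3.0 is dated 17 April 2024, and the last patient was expected out by April 2024.
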